# Tests

As described above three aspects of prosthetic performance determine prosthetic skill. The training programs are focusing on one of the three skills or a combination of all of them (functional). The test tasks differ from the training tasks, though they are based on the same skills. The four test tasks (one for each skill) are used to administer the pretests, posttests and one or two retention tests. During the tests the simulator is worn on the test hand (the 'affected' hand) or, in the case of a patient, the prosthesis is used. During training the simulator is worn on the other, 'unaffected' hand. Below, the four test tasks are described in detail.

[figure not shown]
# Grip force control test tasks

Grip force control in this study is the control of the grip force executed on an object that is grasped by the prosthetic hand. Transfer of force control is found to be possible, though it seems to depend on the situation. Maximal force is shown to transfer in different situations, for example (Farthing, Krentz et al. 2011) grip force control and (Lee, Carroll 2007) maximal acceleration of finger abduction. Transfer of proportional isometric force is only shown between limbs on two sides of the body, not between upper and lower limbs (Christou, Rodriguez 2008). Control of force referred towards the environment (Bensmail, Sarfeld et al. 2010, Chang, Flanagan et al. 2008, Teixeira 2000), like in lifting objects, showed better results than force referred towards maximal output, like giving a percentage of the maximal force (Christou, Rodriguez 2008, Park, Shea 2002).

In an earlier study we found that after training only functional tasks in prosthetic training, force control of the untrained hand did not improve (Romkema, Bongers et al. 2013). It is therefore assumed that force control needs to be trained specifically.

We will therefore use a tracking task. In the tracking task a pattern on the screen needs to be followed for 30 seconds by pressing a handle with the prosthetic hand (Figure 4). The pattern consists of different levels of absolute forces (ranged 5 - 45 N) that vary in a blocked pattern. Each amount of force needs to be hold for two seconds. After each trail the participant is allowed to take a break for a few seconds. The course of the pattern appears slightly (200 ms) before the subject has to produce the force. The pattern starts with a line of three seconds of a force of ten Newton, to make sure that participants are able to position the prosthetic hand on the handle, and that all participants have the same starting position. After these first three seconds the blocked pattern starts.

The dependent variable for this test is the mean deviation of the asked force in N.

*Figure 4.* The line of the asked force (yellow) and produced force (red) that can be seen on the computer screen during the tracking task.

#### Functional test tasks

The functional tasks consist of three object manipulation tasks, as described by Bouwsema (2008). The tasks are based on the three different ways the prosthesis is handled according to van Lunteren et al. (van Lunteren, van Lunteren-Gerritsen et al. 1983); direct grasping, indirect grasping and fixating. In the 'pick-up mug task' the participant has to pick up a mug at the handle with the simulator and to place it 25 cm above the table on a shelf. In the 'lid-off jar task' a jar is picked up by the sound hand at the start and has to be handed over to the simulator, the lid had to be removed by turning it with the sound hand. In the 'zipper task' a pencil case is hold with the simulator at the start position and then the zipper is opened with the sound hand. The dependent variables measured in these tests are the time taken to execute the movement in seconds and the time between the starting signal and the actual start in seconds.

#### Training

During the training sessions of the experimental groups the simulator is worn on the training hand ('unaffected' hand). All training programs are executed during 20 minutes.

#### Grip force control training tasks

To train the control of force three tasks are used: the tracking, the matching and the object task. The tracking task is similar to the test task. A pattern on the screen is followed by squeezing a handle. The pattern now varies, blocked and sinus patterns are used.

For the matching task a handle is squeezed as fast as possible until the amount of force shown on the screen is reached. The force needs to be hold for ten seconds. The amount of force will be shown with a cursor on a line and differs in a range between 5-45 N. After each ten trails the participant will be allowed to take a short break.

In the object tasks deformable objects (Romkema, Bongers et al. 2013) are used. The deformable objects have springs with 5 different resistances. Participants have to pick up objects while trying to compress them as minimally as possible.

#### Functional training tasks

It contains of tasks from the Southhampton hand assessment procedure ((Light, Chappell et al. 2002):

#### Sham group training tasks

The control group executes sham training.

#### **Procedure**

Before the first measurement the Edinburgh Handedness Inventory (Oldfield 1971) is filled in; only right handed participants are included. This questionnaire consists of 10 Items and it takes 1 minute to fill in.

Before each training and test session, a standard protocol is conducted in order to fit the simulator. The simulator is fitted with help of Otto Bock PAULA®. The electrodes within the simulator have to be placed on the optimal locations. The settings need to be tailored to each individual in order to record the myo-electric signal properly. The sensitivity of the electrodes will be adjusted for each participant on each day, so that all participants can just reach the myo-electric threshold of 1.5 V (high signal) and hold it for 2 seconds. The maximum speed of the hand is set to the default setting of 6 (range = 1-6). After the simulator is installed, the participant will be seated at a table and the session will start.

Prior to each task, during the training as well as the tests, the experimenter gives the participant instructions to execute the task. The participants are told to sit comfortably at a table, with their arms resting on the table. They start each task with the prosthetic hand closed. The participants are instructed to execute the tasks as rapidly as possible.

#### Pretest

During all tests we will use the Optotrak system to measure the movements of the arm and prosthesis. Two markers placed on the finger tips of the prosthetic arm; one on the thumb and one on the index finger.

At the first day, the test tasks are administered to determine the level of skills of the participants of the experimental and control groups. This test is performed with the test hand.

#### Training sessions

For the experiment different intervals between the training sessions are used. The training program in which the spacing will be varied is based on the findings of a previous experiment ; the most effective training of this experiment will be chosen to use for the second

Again, the most effective spacing is used in the study on patients.

#### Posttest and retention test

All participants perform a posttest, equal to the pretest. On day 10 and two weeks after the posttest these participants execute a retention test. For both tests the participants again perform the test tasks, in order to determine the improvement of skills and compare the different groups. The tasks are once more presented in a randomized order and executed with the test hand.

#### 8.4 Withdrawal of individual subjects

Participants can leave the study at any time for any reason if they wish to do so without any consequences. The investigator can decide to withdraw a participant from the study for urgent medical reasons. Since the experiments are safe, we do not expect any urgent medical occasions.

#### 8.4.1 Specific criteria for withdrawal (if applicable)

Not applicable

#### 8.5 Replacement of individual subjects after withdrawal

If a participant withdraws from the study, another participant will be asked to join the study, preferably of the same sex.

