# 3. STUDY DESIGN

The experiment aims to reveal the effect of spacing on the intermanual transfer. As found in the available literature, for different tasks, the largest effects are found with a period of minimally 24 hours, the longest period that is tested, between training sessions. Though, the topic of spacing has not received a lot of attention in training motor skills and for periods longer than 24 hours. The sparse evidence revealed that the optimal training effects depend on the nature of the task and on the combination of time interval between the training and the time till the retention test. For this study we therefore choose to use two different time intervals with a minimum of 24 hours. The first group trains daily, the second group trains with two and three days intervals between the training sessions. The training tasks will be chosen based on the previous experiment; the tasks with the largest effects will be used. Two control groups are added both following one of the training shemes of the training groups. These groups will execute a sham training where the wrist muscles are used though the prosthesis is not worn. The tests consists of a pretest, posttest and retention test (seven days after ending the training), to be able to measure whether there were learning effects and whether these effects remained (see 7.3 for an extensive explanation). All tests consist of the same tasks; functional, grip force control, reaching and grasping tasks. Half of the

participants will train their dominant hand and half will train their non-dominant hand. Apart from the three tests, as used in the last experiment, there will be an extra retention test. The first retention test takes place on day 17, so that the first retention test is at the same time interval after the first training for all the spacing regimes. The second retention test is conducted two weeks after the last training session. This will make it possible to show the effects of the different intervals till two weeks after the training.

Healthy adults		i		_				
Spacing	Short inter	rval	Short cont	trol	Long interv	val	Long Cont	trol
Participants	8 men, 8 women (½ dom, ½ n-dom)		8men, 8 women (½ dom, ½ n-dom)		8 men, 8 women (½ dom, ½ n-dom)		8 men, 6 women dom, ½ n-dom)	
Day	Test	Practice	Test	Practice (sham)	Test	Practice	Test	Prac (sha
1 (Mon)	Pretest	30 min	Pretest	30 min	Pretest	30 min	Pretest	30 n
2 (Tue)		30 min		30 min				$\Box$
3 (Wed)		30 min		30 min				

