# 4.4 Sample size calculation

For the second experiment the sample size calculation is done based on the data a previous experiment. The test tasks of the experiment are also used in the first experiment. The participants of both experiments will train on 5 days. We used the pretest and retention test of the force control task to decide what the expected differences are. Using g power we made an estimation of the amount of participants necessary within each group to reach a power of 0.8. Here for we used single side testing with an alfa of 0.05.

Because of the changes for this experiment we can not give an exact estimation. The training will be longer and the tests shorter. We therefore expect the effects to be larger. Though, because we do not have different training tasks but only a difference in spacing we would expect the differences to be smaller.

With the described method we found that we need to have 17 participants in each group (table 5). We would like to make this 16 participants to get an equal distribution of men/women and dominant/not dominant test hand per group.

#### Tabel 5

Sample size per group

		power	pretest	retentietest
Task	Effect size	0.8	deviation	Deviation
Force control	.89	17	7.39	5.04

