#### 8.6 Follow-up of subjects withdrawn from treatment

Not applicable

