#### 10.4 Analysis (if applicable)

In the experiments all measurements (deviation of grip force control, deviation of straight reaching path, length of plateau phase in grasping and movement time) are subjected to a repeated-measures ANOVA with test (pre-test, post-test and retention test(s)) as within-subject factor and dominance (preferred, non-preferred) and group (two experimental groups, two control groups) as between-subject factors.

When a Mauchly test indicates that sphericity is violated, the degrees of freedom are adjusted with the Greenhouse-Geisser correction. In all analyses, a significant criterion of  $\alpha$  less than or equal to 0.05 is used, and post hoc tests on main effects use Bonferroni adjustment.

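### Withdrawn participants are replaced and the planned ANOVA needs every test, so the analysis as written rests on completers, and time at risk of dropout differs between the two spacing schedules

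*Protocol*

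**What the plan says.** Leaving is unrestricted (section 8.4): "Participants can leave the study at any time for any reason if they wish to do so without any consequences". Section 8.5 then provides: "If a participant withdraws from the study, another participant will be asked to join the study, preferably of the same sex". It sets no limit by timing or reason, and does not say which group the newcomer joins or what happens to data already collected. The next section, "8.6 Follow-up of subjects withdrawn from treatment", is marked not applicable.

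Section 10.4 subjects all four main endpoints to a "repeated-measures ANOVA with test (pre-test, post-test and retention test(s)) as within-subject factor", with group and dominance as between-subject factors, a Mauchly test and a Greenhouse-Geisser correction. It names no analysis population.

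On the schedule, section 3 states: "The first group trains daily, the second group trains with two and three days intervals between the training sessions". It adds: "The second retention test is conducted two weeks after the last training session". Table 2 puts the posttest on day 5 in the short groups and day 15 in the long groups, a retention test on day 17 in all groups, and the last test on day 19 (short) or day 29 (long).

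**The concern.** A repeated-measures ANOVA with sphericity testing works on complete rows. A participant who leaves after the posttest gives two usable measurements, yet contributes nothing to it. If each leaver is also replaced, the table can fill to 16 per group while consisting of people who finished, not of the people randomised.

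That matters most where the chance of leaving differs between the groups compared. Here the schedule itself sets different lengths of participation, and schedule is the randomised factor of interest. If leaving is related to performance, the short-versus-long contrast compares two differently selected sets of completers. Unless withdrawals are reported by group, the reader also cannot see whether one schedule was harder to complete, which is relevant because section 1 studies longer intervals for their practicality in rehabilitation.

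**Working it through.** **1. The plan's own figure.** Section 4.4 gives effect size 0.89, power and alpha as follows: "to reach a power of 0.8" and "Here for we used single side testing with an alfa of 0.05". For a one-sided two-sample t-test the noncentrality is d × √(n/2).
- n = 17: 0.89 × √8.5 = 2.59, power 0.814.
- n = 16: 0.89 × √8 = 2.52, power 0.792.

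So 17 per group reproduces, and 16 falls just short of 0.8. The calculation has no allowance for dropout; replacement does that job.

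**2. Time at risk (section 3, Table 2).**
- Pretest to last test: 19 − 1 = 18 days (short); 29 − 1 = 28 days (long). Ratio 28/18 = 1.56.
- Pretest to posttest: 5 − 1 = 4 days; 15 − 1 = 14 days. Ratio 3.5.
- Pretest to first retention test: 17 − 1 = 16 days in all groups.
- Visits: short on days 1 to 5, 17 and 19; long on days 1, 4, 8, 11, 15, 17 and 29. Seven each.

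The ANOVA needs all tests, so the window that matches it is 18 versus 28 days. Section 8.3 puts the first retention test on day 10, against day 17 in section 3 and Table 2. Those passages must be reconciled, but the 10-day gap at the last test is unaffected.

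**3. Dropout under an equal daily hazard (assumption; no rate is given).** If a proportion p leaves a short group over 18 days, the long-group proportion is 1 − (1 − p)^(28/18).

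| Short group | Long group | Expected leavers of 16, short / long |
|---|---|---|
| 5% | 7.7% | 0.8 / 1.2 |
| 10% | 15.1% | 1.6 / 2.4 |
| 20% | 29.3% | 3.2 / 4.7 |

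**4. Distortion of the short-versus-long contrast.** Suppose leaving follows a latent normal variable correlated ρ with the outcome. The completer mean then shifts by ρ × φ(z_p)/(1 − p) SD, where z_p is the normal quantile at p and φ the normal density. The distortion is the long-group shift minus the short-group shift. For p = 10% the factor φ/(1 − p) is 0.195 (short) and 0.276 (long), a difference of 0.081.

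| Short-group dropout | ρ = 0.3 | ρ = 0.5 |
|---|---|---|
| 5% | 0.014 SD | 0.024 SD |
| 10% | 0.024 SD | 0.041 SD |
| 20% | 0.041 SD | 0.068 SD |

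At 16 per group, a two-sided 5% two-group t-test with no true difference rejects 5.0% to 5.4% of the time under shifts of this size.

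**5. One-sided selective dropout (extreme case).** Suppose k of 16 leave one group and none leave the other. With ρ = 1 (exactly the worst performers leave), p = 1/16, 2/16 and 3/16 give shifts of 0.131, 0.235 and 0.331 SD. With ρ = 0.5 these halve to 0.07, 0.12 and 0.17 SD. At shifts of 0.12, 0.235 and 0.33 SD the same t-test rejects about 6%, 10% and 15% of the time. The 2-of-16 case is 13% (0.12/0.89) to 26% (0.235/0.89) of the planning effect.

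The rejection rates are for a plain two-group comparison, not the four-group repeated-measures model.

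**The case against.** The strongest reply is that completers-only analysis is an inference. Section 8.5 says only that someone else is asked to join; it does not say that the leaver's data are discarded, and a SAP could name an analysis set. This is right about the wording. What stands is that replacement, no follow-up of withdrawals and a classical ANOVA are each fixed in the protocol, and together they have that effect.

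Four stronger readings are tempting but not supported:
- **That missing one retention test triggers replacement.** Section 8.5 applies to withdrawal from the study. A missed test alone costs the participant's row in the ANOVA, but does not bring in a substitute.
- **That exposure is 3.5 times as long in the long groups.** This holds only up to the posttest. Over the window that the ANOVA uses it is 1.56 times, with a shared day-17 test and equal visit counts.
- **That the long schedule would be made to look better.** Nothing shows that it is harder to complete; five consecutive days may be as demanding as five spread-out ones.
- **That replacement creates the bias.** The shift comes from selective dropout and would arise in a completer analysis without replacement. Replacement restores the numbers.

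Two further points stand in part. Each schedule has its own sham group on the same calendar, so dropout driven by the calendar partly cancels in training-minus-sham contrasts, fully only if trained and sham participants leave for the same reasons. Sections 12.2 and 12.4 provide for weekly monitoring and for reporting numbers included and completed to the ethics committee, though not by group.

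**Conclusion.** The point holds as a weakness in how the analysis set arises, not as evidence of large bias. Followed as written, the plan analyses completers and discards partial data from randomised participants, and the contrast that answers the trial's question is the one with unequal time at risk.

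Under equal daily hazard and modest correlation the distortion is about 0.01 to 0.07 SD, which is small beside 0.89. Section 4.4 itself expects smaller differences in this experiment because only spacing varies, so 0.89 is a generous yardstick. Distortion of 0.13 to 0.33 SD needs the worst performers to leave one group while nobody leaves the other. All of these figures rest on assumed dropout rates and correlations, since the protocol gives none. The change is worth making because it is cheap and removes a dependence on those assumptions that cannot be checked afterwards if withdrawals are not reported by group.

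**What to change.** In section 8.5, state that a replacement is additional and does not substitute: every randomised participant stays in the analysis, in the assigned group, with all tests completed.

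In section 10.4, fit the same factors (test, group, dominance and their interactions) as a linear mixed model for repeated measures, which uses partial records. Keep the complete-case ANOVA as a sensitivity analysis, and report withdrawals by group and by time of leaving.

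Restricting replacement to those who leave before the posttest is not advised, because it would tie the rule to the most unequal window (4 versus 14 days).

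The cost is wording in two sections and a little more analysis work, with no added visits. Group sizes may become slightly unequal. The mixed model assumes that missingness is explained by the observed data; it will not remove bias from loss of interest that leaves no trace in earlier tests.

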#### 8.6 Follow-up of subjects withdrawn from treatment

Not applicable

# 8.7 Premature termination of the study

Not applicable

# 9. SAFETY REPORTING

# 9.1 Section 10 WMO event

In accordance to section 10, subsection 1, of the WMO, the investigator will inform the participants and the reviewing accredited METC if anything occurs, on the basis of which it appears that the disadvantages of participation may be significantly greater than was foreseen in the research proposal. The study will be suspended pending further review by the accredited METC, except insofar as suspension would jeopardise the participants' health. The investigator will take care that all participants are kept informed.

# 9.2 AEs, SAEs and SUSARs

# 9.2.1 Adverse events (AEs)

Adverse events are defined as any undesirable experience occurring to a subject during the study, whether or not considered related to the experimental intervention (e.g. prosthetic simulator training or testing). All adverse events reported spontaneously by the subject or observed by the investigator or his staff will be recorded.

# 9.2.2 Serious adverse events (SAEs)

A serious adverse event is any untoward medical occurrence or effect that at any dose: results in death;

- is life threatening (at the time of the event);
- requires hospitalisation or prolongation of existing inpatients' hospitalisation;
- results in persistent or significant disability or incapacity;
- is a congenital anomaly or birth defect;

Any other important medical event that may not result in death, be life threatening, or require hospitalization, may be considered a serious adverse experience when, based upon appropriate medical judgement, the event may jeopardize the subject or may require an intervention to prevent one of the outcomes listed above.

The investigator is responsible for reporting all SAE's to the sponsor. This is independent of the centre where the research takes place. The sponsor will report the SAEs through the web portal ToetsingOnline to the accredited METC that approved the protocol, within 15 days after the sponsor has first knowledge of the serious adverse reactions.

SAEs that result in death or are life threatening should be reported expedited. The expedited reporting will occur not later than 7 days after the responsible investigator has first knowledge of the adverse reaction. This is for a preliminary report with another 8 days for completion of the report.

